E-mail Correspondence with the Food and Drug Administration (FDA) regarding an exemption for an Investigational New Drug (IND) Application

From: xxx

Sent: Friday, April 05, 2013 8:23 AM

To: xxx

Cc:

Subject: FW: Rectal Indomethacin for Patients Undergoing ERCP

Dear xxx:

We have received, on March 19, 2013, your e-mail dated March 19, 2013, for Indocin Suppositories. This submission contains a protocol titled, "Rectal Indomethacin in the Prevention of Post-ERCP Pancreatitis in High Risk Patients: Searching for the Optimal Dose. A Prospective, Randomized Trial" and a request for exemption from the requirement to conduct the study under an Investigational New Drug Application.

After reviewing the information contained in your submission, we have concluded that your study meets all of the requirements for exemption from the IND regulations and, therefore, an IND is not required to conduct your investigation.

**Rectal Indomethacin in the Prevention of
Post- ERCP Pancreatitis in High Risk Patients:
Searching for the Optimal Dose.
A Prospective, Randomized Trial**

Protocol Version 8.0

**[name]
Professor of Medicine
Indiana University**

[name]
Assistant Professor of Medicine
University of Michigan

[name]
Professor of Medicine
University of Michigan

[name]
Professor of Medicine
University of Michigan

[name]
Clinical Associate Professor of Medicine
University of Wisconsin

[name]
Professor of Medicine
Indiana University

[name]
Professor of Medicine
Indiana University

[name]
Clinical Associate Professor of Medicine
University of Texas Southwestern

B. [name]
Associate Professor of Internal Medicine
Medical University of South Carolina

A. Objective: To compare the efficacy of two different dose regimens of prophylactic rectally-administered indomethacin on the incidence on post-endoscopic retrograde pancreatography (ERCP) pancreatitis (PEP) in high-risk patients.

B. Hypotheses and Specific Aims

H1 (primary): A higher peri-procedure dose of rectal indomethacin at ERCP will reduce the incidence of PEP in high risk patients, compared with standard dosing.

H2 (secondary): A higher peri-procedure dose of rectal indomethacin at ERCP will reduce the incidence of moderate to severe PEP in high risk patients, compared with standard dosing.

SA1 (primary): To perform a prospective, randomized, double-blind clinical trial comparing a higher dose indomethacin regimen to standard dosing in preventing PEP in high-risk patients.

SA2 (secondary): In the same format as SA1, to compare a higher dose indomethacin regimen to standard dosing in preventing moderate to severe PEP in high-risk patients.

C. Background, preliminary data, and significance

Pancreatitis is the most frequent complication of endoscopic retrograde cholangiopancreatography (ERCP), accounting for substantial morbidity, occasional mortality, and increased health care expenditures (1-3). Multiple pharmacologic agents have been evaluated in the prevention of post-ERCP pancreatitis (PEP) (4). Recently, interest has developed in the study of non-steroidal anti-inflammatory drugs (NSAIDs) for the prevention of PEP. Mechanistically, NSAIDs are potent inhibitors of phospholipase A2, prostaglandins, and neutrophil/endothelial interaction, all believed to play an important role in the pathogenesis of acute pancreatitis (5-7). Animal models have demonstrated that NSAIDs can reduce mortality associated with pancreatitis (8-10) and a small human trial of indomethacin in non-ERCP acute pancreatitis showed improvement in clinical outcomes (11).

NSAIDs are attractive in the pharmacologic prevention of PEP because they are widely available, inexpensive, and easily administered. In addition, they appear to have a favorable risk profile when given as a one-time dose to appropriately selected patients. Prospective clinical trials evaluating the use of NSAIDs in ERCP have shown that the incidence of adverse events attributable to NSAIDs, including post-procedure hemorrhage, is equivalent in the NSAIDs and placebo groups (12-17). This observation is congruent with previously published data suggesting that NSAIDs in standard doses do not increase the risk of significant bleeding after biliary sphincterotomy (3,18).

Several prospective clinical trials have evaluated rectal NSAIDs in the prevention of PEP (12-15,17). Murray et al. (12) demonstrated a statistically significant benefit of rectal diclofenac in 220 patients who either underwent pancreatography or had manometrically documented sphincter of Oddi dysfunction (SOD). Conversely, Sotoudehmanesh et al. (13) failed to show prophylactic benefit of rectal indomethacin in 442 mostly low-risk patients. A *post hoc* subgroup analysis of this study, however, did reveal a protective effect in patients undergoing pancreatic duct injection, although the power of this subgroup was insufficient to draw concrete clinical conclusions. Khoshbaten et al. (14) showed a statistically significant benefit of rectal diclofenac in 100 patients undergoing pancreatography and Montano Loza et al. (15) also demonstrated a benefit in 150 patients at low-risk for PEP receiving rectal indomethacin or placebo. A meta-analysis of these four studies evaluating rectal NSAIDs in preventing post-ERCP pancreatitis revealed a statistically significant 64% reduction in PEP, with a number needed to treat to prevent one episode of pancreatitis of 15 patients (19). Although the results of this meta-analysis were encouraging, several limitations were noted. First, the component studies enrolled patients at variable risk for PEP. As such, it remained unclear from these data whether rectal NSAIDs were effective in both high and low risk patients, and if so, which group derived the most favorable risk & cost-benefit ratios. Second, the meta-analysis included outcomes from studies evaluating either diclofenac or indomethacin. While these drugs demonstrate similar

phospholipase A2 inhibition in vivo, it remains unclear if both drugs are independently clinically effective (20,21). Moreover, prior positive meta-analyses of prophylactic agents in preventing PEP have subsequently been disproved by additional rigorous clinical investigation (22,23). Therefore, a definitive clinical trial evaluating rectal indomethacin in the prevention of PEP was needed to confirm the results of the meta-analysis (19) and establish a concrete role for prophylactic rectal NSAIDs in clinical practice.

In order to specifically address this issue, Elmunzer and colleagues recently evaluated the role of rectal indomethacin in the prevention of PEP in high-risk patients (17). This multicenter, randomized, placebo-controlled, double-blind clinical trial assigned high-risk patients (82% had suspected or confirmed SOD) to receive a single dose (100mg) of rectal indomethacin or placebo (a glycerin suppository) immediately after ERCP. Post-ERCP pancreatitis developed in 27/295 patients (9.2%) in the indomethacin group compared with 52/307 (16.9%) in the placebo group ($p=0.005$). This beneficial effect of indomethacin was seen across all subgroups analyzed. Furthermore, moderate-to-severe pancreatitis rates were significantly lower in the indomethacin group (4.4% vs 8.8%, $p=0.03$). Adverse events were uncommon, as clinically significant bleeding occurred in 4 patients in the indomethacin group and 7 patients in the placebo group ($p=0.72$). Two cases of acute renal failure occurred, both in the placebo group. While confirmatory data would be of interest, indomethacin appears to be the first unequivocally effective pharmacologic agent in the prevention of PEP in high-risk patients. Indeed, anecdotal data currently suggest that indomethacin is being increasingly adopted into widespread clinical use for the prophylaxis of PEP.

While the beneficial effect of indomethacin as demonstrated by Elmunzer et al. (17) represents a major advancement in PEP prevention, pancreatitis rates remain unacceptably high in high-risk patients -- nearly 10% in this study which took place in academic centers with experienced endoscopists. When used as an analgesic or anti-inflammatory agent in the management of patients with arthritis (gout, rheumatoid, ankylosing spondylitis), the recommended maximal daily dose of indomethacin is 200 mg per day, in divided doses (product insert, Merck & Co.). The half-life of this agent is approximately 4.5 hours. Potentially, a higher dose of indomethacin, perhaps leading to a higher peak serum concentration, might further lower PEP rates in high-risk patients. Alternatively, a second dose of the drug might lead to a more sustained effect. We acknowledge that there are no pharmacokinetic data to confirm or substantiate these hypotheses. If either of these phenomena is important in pancreatitis prevention, then a regimen consisting of a higher initial dose followed by a second dose may be hypothesized to be superior.

While all patients undergoing ERCP may benefit from the protective effect of indomethacin, the incidence of pancreatitis in high-risk patients is such that prevention of PEP in this patient population would lead to the most substantial reduction in morbidity and health care costs. Moreover, the elevated baseline risk of PEP in high-risk patients makes clinical trials in this group more feasible due to more manageable sample sizes.

Our objective is to perform a prospective, randomized, double-blind trial evaluating two different dose regimens of rectal indomethacin in the prevention of PEP. While a single 100 mg dose (the "standard" dose) is effective in high-risk patients (17), the ideal or most efficacious dose regimen is unknown. This study will determine which dose regimen of rectal indomethacin is more effective in preventing post-ERCP pancreatitis. The results will help the research team determine whether there is reason to continue this line of research or whether it would be better to focus on a different area (perhaps use of another class of drugs or a device).

D. Sample size calculation:

An internal audit of high-risk ERCPs at the four tertiary referral centers involved in this clinical trial reveals a PEP rate of approximately 10%, despite the routine use of prophylactic pancreatic duct stent placement (24-26) in appropriate patients and selective use of indomethacin. It is anticipated that the patient characteristics/demographics in this study will be very similar to that of Elmunzer et al. (17), as inclusion and exclusion criteria will be the same (see below). In that study (17), the PEP rate in patients who received indomethacin 100 mg was 9.2%. To achieve a 50% reduction in the rate of PEP (i.e. to 4.6%), with two-sided $\alpha=0.05$ and a power of 0.8, the necessary sample size is 1036. This absolute reduction in incidence

is felt to be clinically relevant and substantial enough to change existing clinical practice.

E. Methodology- Design and procedures

This study is designed as a prospective, randomized, double-blind clinical trial. We plan on enrolling 1036 high-risk patients undergoing ERCP. These patients will be enrolled at six tertiary care hospitals in the United States: Indiana University Hospital (Indianapolis, IN), University of Michigan Medical Center (Ann Arbor, MI), Methodist Dallas Medical Center (Dallas, TX), Aurora St. Luke's Medical Center (Milwaukee, WI), the Medical University of South Carolina (Charleston, SC), and Beth Israel Deaconess Medical Center (Boston, MA). The study will be conducted after approval from the internal review committees of all participating institutions. We have been granted an IND exemption from the Food and Drug Administration for this protocol (see attached).

Patients, study personnel, and treating physicians will be blinded to study group assignment. The randomization schedule, which is stratified according to study center, will be generated centrally at the University of Michigan and distributed to the other study sites. The randomization schedule will be kept by personnel not directly involved with the study. This same personnel will be responsible for packaging the drug and placebo. Based on current annual procedure volume, it is assumed that 700 patients will be recruited by the Indiana University site, with 336 patients recruited by the other sites. These estimates are not binding, as all sites will be allowed to continue recruiting patients until the recruitment goal is met, or interim analyses suggest early study termination. The individual sites will order the indomethacin suppositories as necessary through the research coordinator at Indiana University, as determined by their recruitment rate. The exception to this is MUSC will be ordering indomethacin suppositories on their own, which will come from the same manufacturer, G and W laboratories, that all other sites are using. The glycerin suppositories will be obtained either by each institution's standard ordering procedure, or by ordering from Indiana University. If ordering from Indiana University, the suppositories will be shipped directly to each individual site.

Inclusion criteria:

The inclusion criteria are intended to select a group of patients at high-risk (approximately 10%) for post-ERCP pancreatitis. These criteria are based on patient and procedure-related risk factors that have been previously shown in multivariable analyses to confer a significantly increased risk of PEP.

Included patients are those undergoing ERCP and have:

one of the following:

- 1) Suspected sphincter of Oddi dysfunction, type I or type II
- 2) History of post-ERCP pancreatitis (at least one episode)
- 3) Pancreatic sphincterotomy
- 4) Pre-cut (access) sphincterotomy
- 5) > 8 cannulation attempts of any sphincter
- 6) Pneumatic dilation of intact biliary sphincter
- 7) Ampullectomy
- 8) Assessment for post-sphincterotomy stenosis

or **at least 2** of the following:

- 1) Age < 50 years old and female gender
- 2) History of recurrent pancreatitis (at least 2 episodes)
- 3) ≥3 pancreatic injections, with at least one injection to tail
- 4) Pancreatic acinarization (excluding ventral pancreas of pancreas divisum)

5) Pancreatic brush cytology.

Exclusion criteria:

- 1) Unwillingness or inability to consent for the study
- 2) Age < 18 years
- 3) Intrauterine pregnancy
- 4) Breastfeeding mother
- 5) Standard contraindications to ERCP
- 6) Allergy / hypersensitivity to aspirin or NSAIDs
- 7) Received NSAIDs in prior 7 days (aspirin 325 mg or less OK)
- 8) Renal failure (Cr > 1.4)
- 9) Active or recent (within 4 weeks) gastrointestinal hemorrhage
- 10) Acute pancreatitis (lipase peak) within 72 hours
- 11) Known chronic calcific pancreatitis
- 12) Pancreatic head mass
- 13) Procedure performed on major papilla/ventral pancreatic duct in a patient with pancreas divisum (dorsal duct not attempted or injected)
- 14) ERCP for biliary stent removal or exchange without anticipated pancreatogram
- 15) Subject with prior biliary sphincterotomy now scheduled for repeat biliary therapy without anticipated pancreatogram
- 16) Anticipated inability to follow protocol
- 17) Known active cardiovascular or cerebrovascular disease

Protocol:

Subjects who do not meet any exclusion criteria may be consented for the trial by a clinical research coordinator or one of the investigators. The consent process will occur prior to ERCP in the procedure preparation area. At this time, the objectives of the study as well as the risks and benefits of enrolling will be explained in detail to potential subjects.

After obtaining informed consent, subjects will undergo ERCP per clinical protocol. All procedure-related clinical decisions and interventions will be dictated by the performing physician as he or she sees fit. At the end of the procedure, it will be determined by the endoscopist and research coordinator whether the patient meets inclusion criteria. If inclusion criteria are met, subjects will be randomized by concealed allocation to receive either 100 mg or 150 mg indomethacin, in the form of two or three 50 mg identical-appearing rectal suppositories. Those patients who are randomized to receive the 100 mg dose will receive an additional glycerin suppository. The suppositories will be placed while the patient is still sedated in the ERCP suite, prior to transfer to the recovery area. Four hours later (+/- 20 minutes), those patients who were randomized to the high-dose group (already received 150 mg dose) will then receive an additional 50 mg suppository while in the recovery area. At this same time point, subjects who were randomized to the standard-dose group (already received 100 mg dose) will receive a glycerin suppository in the recovery area. All participating patients, therefore, will receive a total of 4 suppositories, as summarized below:

	Immediately post-ERCP	4 hours post-ERCP
High dose	Indomethacin 150 mg (50 mg x 3)	Indomethacin 50 mg x 1
Standard dose	Indomethacin 100 mg (50 mg x 2) + glycerin x1	glycerin x 1

There will be one source of indomethacin suppositories for all six participating sites. G and W Laboratories, Inc., South Plainfield, NJ 07080 will manufacture the indomethacin suppositories. The suppositories will then be distributed by IROKO Pharmaceuticals, LLC, Philadelphia, PA 19112.

Indomethacin and glycerin suppositories will be packaged according to the randomization schedule by personnel not directly involved in the conduct or interpretation of the study. The study package for each subject will be an opaque envelope or bottle. High-dose packages will contain 2 small plastic bags: bag #1 containing 3 indomethacin suppositories and bag #2 containing 1 indomethacin suppository. Standard dose packages will contain 2 small plastic bags: bag #1 containing 2 indomethacin suppositories and 1 glycerin suppository and bag #2 containing 1 glycerin suppository. The package will be fully opaque such that the contents of cannot be discerned without opening the envelope or bottle.

Since there are differences in the appearance of the indomethacin and glycerin suppositories, they will only be administered by clinical nurses not involved in the study. Immediately after ERCP, the clinical nurse will be instructed to deliver contents of bag #1 and the sealed package will be returned to the study coordinator, who will instruct a clinical nurse to deliver the contents of bag #2 approximately four hours after the procedure.

The packages will be stored in a clinical refrigerator prior to administration of bag #1 and between administration of bags #1 and #2.

Pancreatic duct stent placement will be at the discretion of the endoscopist on a case-by-case basis, as patients enrolled in this study will be considered to be at high-risk for PEP. The manufacturer, length, and caliber of prophylactic pancreatic stents will also be left to the discretion of the endoscopist, reflecting the variability in clinical practices in this area.

At our institutions, subjects are observed in the recovery area for approximately 4 hours after the termination of the procedure. Patients who develop abdominal pain (or worsening of their baseline abdominal pain) during this observation period are generally admitted to the hospital (for current inpatients, kept in the hospital) in order to exclude procedural complications, including pancreatitis and perforation. The decision to admit the patient or prolong existing hospitalization will be left to the discretion of the endoscopist and clinical service, respectively. Those patients who are hospitalized will have serum amylase and lipase drawn at least once 24 hours after the procedure and subsequently at the discretion of the clinical service. Patients who are discharged uneventfully after ERCP will be contacted by telephone or email within 5 ± 2 days of the procedure by a study team member to evaluate for the development of post-ERCP pancreatitis and other related or unrelated complications. All subjects will also be contacted 30 ± 5 days by telephone or email after the procedure to verify that information about complications has been captured, particularly bleeding which can be delayed after ERCP. Definitions: PEP will be defined per consensus guidelines (27): 1) New or increased abdominal pain that is clinically consistent with a syndrome of acute pancreatitis **and** 2) amylase or lipase $\geq 3x$ the upper limit of normal 24 hours after the procedure **and** 3) Hospitalization (or prolongation of existing hospitalization) for at least 2 days (at least night of ERCP & next night). Mild PEP will be defined as pancreatitis that results in hospitalization (or prolongation of existing hospitalization) for ≤ 3 days. Moderate PEP will be defined as pancreatitis that results in hospitalization (or prolongation of existing hospitalization) for 4-10 days. Severe PEP will be defined as pancreatitis that results in hospitalization (or prolongation of existing hospitalization) for > 10 days, or leads to the development of pancreatic necrosis or pseudocyst, or requires additional endoscopic, percutaneous, or surgical intervention.

Data management:

Patient demographics, risk factors, the procedural elements of the ERCP, and follow-up data will be

recorded on a standardized data collection form at the time of the procedure and within 5 days and 30 days after the procedure. This information will be recorded by a research coordinator. All completed data collection forms from the University of Michigan Medical Center, Methodist Dallas Medical Center, Aurora St. Luke's Medical Center, the Medical University of South Carolina, and Beth Israel Deaconess Medical Center will be faxed, emailed, or uploaded into MiShare and sent to IU. The data will be transferred by the IU study coordinator to a master excel database, housed on a password protected desktop computer in a locked research office. A second research team member from IU will perform data entry confirmation.

F. Statistical analysis

For the analysis of the primary endpoint, the difference in the proportion of patients developing post-ERCP pancreatitis between the two groups will be analyzed using a two-tailed Fisher's exact test, with a two-sided $p < 0.05$ indicating statistical significance.

After enrolling 400 patients (37.7% of total enrollment) a BLINDED interim analysis will be conducted by the independent DSMB as follows. For each subject the DSMB will be provided with 1) the subject ID number, 2) whether or not the primary endpoint (post-ERCP pancreatitis) occurred, 3) whether or not a bleeding event occurred, and 4) in which group (high-dose or standard dose regimen) the patient belonged. If $> 66\%$ of the pancreatitis cases or bleeding cases are in a particular group (high-dose or standard dose regimen), the DSMB will break the code to determine whether these events are in the standard 100 mg indomethacin group or high-dose indomethacin group. This value was selected because it represents a 2:1 (double) frequency of an endpoint outcome in one group or another. If either of these events has occurred at this high frequency in one group or another, then the DSMB will decide that the study should be stopped. Even if the DSMB is required to break the code for this above listed purpose, the investigators will never be aware of this information. The DSMB will simply tell the investigators whether or not to continue the study. If during this blinded interim analysis, the DSMB finds that the proportion of the patients with pancreatitis in the higher dose indomethacin group is significantly lower, a formal statistical analysis will be performed and statistical significance will only be declared (and the study terminated) if the two-sided p value is less than 0.005. In this unlikely circumstance, the DSMB will inform the investigators that the study should be terminated for ethical reasons (i.e., it would be unethical to withhold this from high-risk patients).

After enrolling 600 subjects (56.6% of total enrollment) a BLINDED interim analysis will be conducted by the independent DSMB as follows. For each subject the DSMB will be provided with 1) the subject ID number, 2) whether or not the primary endpoint (post-ERCP pancreatitis) occurred, 3) whether or not a bleeding event occurred, and 4) in which group (high-dose or standard dose regimen) the patient belonged. This analysis will be performed because it was a specific request of the DSMB that it be performed to ensure the safety of subjects. Analysis and criteria for stopping the study at this second interim analysis will be the same as those noted above, for the first interim analysis.

For the analysis of the secondary endpoint, the difference in the proportion of patients developing moderate-severe PEP between the two groups will be analyzed using a two-tailed Fisher's exact test.

An additional secondary analysis will include the multivariate evaluation of the prediction of PEP by treatment arm while controlling for covariates, which we expect may contribute to the variance in PEP incidence. These covariates will include:

Clinical suspicion of sphincter of Oddi dysfunction
Age
Gender
Race
Body mass index
History of recurrent pancreatitis (at least 2 episodes)
History of post-ERCP pancreatitis (at least one episode)

Pancreatic sphincterotomy
Pre-cut (access) sphincterotomy
Number of cannulation attempts
Number of pancreatic injections
Pneumatic dilation of intact biliary sphincter
Ampullectomy
Pancreatic brush cytology
Pancreatic acinarization
Cardioprotective aspirin use
Pancreatic duct stent placement
Use of double wire cannulation technique
Trainee involvement in procedure
Biliary sphincterotomy
Prophylactic pancreatic stent characteristics (manufacturer/length/caliber)
Type of sphincter of Oddi dysfunction (suspicion, pre-manometry)
Inpatient vs. outpatient status
Participating medical center

We realize that the event rate may be too low to include more than a few variables in the multivariate model. Based on univariate analysis of each variable in predicting PEP, we will include no more than one variable per 10 PEP events in the final multivariate model predicting PEP.

Exploratory subgroup analyses will also be performed on the following pre-specified characteristics: age, gender, race, body mass index, suspicion of sphincter of Oddi dysfunction, prior post-ERCP pancreatitis, history of recurrent pancreatitis, manometrically documented sphincter of Oddi dysfunction, difficult cannulation, pre-cut (access) sphincterotomy, pancreatic sphincterotomy, pancreatic acinarization, biliary sphincterotomy, double wire cannulation technique pancreatic stent placement, trainee involvement, cardioprotective aspirin use, prophylactic pancreatic stent characteristics, type of sphincter of Oddi dysfunction, inpatient vs. outpatient status, and participating medical center. These subgroup analyses will allow the development of hypotheses regarding which subgroups of patients, if any, may particularly benefit from a more intensive indomethacin regimen.

Further, we will perform a heterogeneity in treatment effects analysis on enrolled subjects according to their pre-treatment risk of post-ERCP pancreatitis, functionally assessing whether the relative treatment effect is consistent across the spectrum of study subjects' risk of post-ERCP pancreatitis. Individual subject risk scores will be calculated by assigning one point for each major inclusion criterion and 0.5 points for each minor inclusion criterion, as previously reported (17).

It is recognized that some patients may have difficulty holding their suppositories, and expulsion of the suppositories may or may not be witnessed by study personnel. All patients will be analyzed on an intent-to-treat basis, in the group to which they were randomized. However, we anticipate that this point will have little impact on study outcome, as indomethacin suppositories dissolve quickly (rather than melt slowly) and are seldom recovered in recognizable form if the patient retains the suppository for more than a few minutes (product insert, Merck & Co.). If a suppository is recovered in visible and intact form, it may be re-inserted.

G. Budget

Funding for this study has been obtained from the American College of Gastroenterology. The Clinical Research Award amount is \$34,975 which will be used for medication costs for all sites, as well as coordinator support at Indiana University.

References:

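### Randomization is stratified by center, but both pancreatitis comparisons pool centers in a Fisher's exact test and no confidence interval is planned: a cheap improvement, not an error

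*Combined protocol and SAP*

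**What the plan says.** Section E (design and procedures): "The randomization schedule, which is stratified according to study center, will be generated centrally". There are six sites of very unequal size: "it is assumed that 700 patients will be recruited by the Indiana University site, with 336 patients recruited by the other sites".

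Section F (statistical analysis), on the main comparison: "the difference in the proportion of patients developing post-ERCP pancreatitis between the two groups will be analyzed using a two-tailed Fisher's exact test", judged at a two-sided 0.05. The secondary comparison is planned the same way: "the difference in the proportion of patients developing moderate-severe PEP between the two groups will be analyzed using a two-tailed". The test named there is again Fisher's. Neither test uses center. No confidence interval is mentioned anywhere in the plan.

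Center appears in two other places in Section F. It is the last of 24 candidate covariates in the multivariate model, where selection works as follows: "Based on univariate analysis of each variable in predicting PEP, we will include no more than one variable per 10 PEP events". It is also one of the exploratory subgroup factors.

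The interim analyses at 400 and 600 patients bear on any change of test. The efficacy test there is triggered in one direction only: "the proportion of the patients with pancreatitis in the higher dose indomethacin group is significantly lower, a formal statistical analysis will be performed". Its threshold is stricter than the final one: "statistical significance will only be declared (and the study terminated) if the two-sided p value is less than 0.005". The test to be used at the looks is not named. Separately, if more than 66% of pancreatitis or bleeding cases fall in one arm, "then the DSMB will decide that the study should be stopped".

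**The concern.** An analysis normally reflects the factor by which patients were randomized. Here the stratification factor enters neither main comparison, and it may drop out of the multivariate model too, because entry depends on univariate screening under a tight cap.

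Two things are at stake. First, Fisher's exact test leaves part of the permitted 0.05 unused, so the same patients could yield somewhat more power, most visibly on moderate-severe PEP. Second, a p-value alone says little if the result is not significant: without an interval, a reader cannot tell whether a worthwhile reduction has been ruled out. Section C says the results are meant to guide whether this line of research continues, and that decision needs an interval.

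**Working it through.** **Inputs.** From Section D: PEP 9.2% on standard dose, 4.6% on high dose, two-sided 0.05, power 0.80, N = 1036. From Section E: 700 patients at the largest site, 336 at the other five. From Section C: moderate-to-severe PEP 4.4% on 100 mg. Assumed: 1:1 allocation (no ratio is stated, but 1:1 reproduces N); the 336 split about equally, giving per-arm center sizes 350, 34, 34, 34, 33, 33; risk halved in every center; moderate-severe PEP falling to 2.2% (the plan gives no target). The documents give no center-specific PEP rates, so five patterns averaging 9.2% were tried.

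**1. The plan's own sample size.** The mean rate is 0.069 and the difference is 0.046.

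- Uncorrected: n = [1.960·√(2·0.069·0.931) + 0.842·√(0.092·0.908 + 0.046·0.954)]² / 0.046² = 475.4 per arm.
- Continuity-corrected: (n/4)·[1 + √(1 + 4/(n·0.046))]² = 517.9, so 518 per arm and 1036 in total.

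The stated figure is reproduced by the formula that suits Fisher's test.

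**2. Pooled tests, exact enumeration at 518 per arm.**

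- Power at 9.2% vs 4.6%: Fisher 81.0%, uncorrected Pearson chi-square 83.9%.
- True size of Fisher: 0.0359, 0.0378, 0.0395 and 0.0396 at common rates of 4.6%, 6.9%, 9.2% and 10%.

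**3. Center-stratified test, simulated (400,000 trials).** In center k, let x be the standard-dose events, t all events, n the patients per arm and N = 2n. Then CMH = [Σ(x − t/2)]² / Σ[n²·t·(N − t) / (N²(N − 1))], without continuity correction. The last three columns add the two 0.005 looks, counted only when PEP is lower on high dose, and ignore the >66% rule.

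| Standard-dose PEP rates | Pearson, single test | CMH, single test | Due to stratifying | Fisher with looks, final 0.05 | CMH with looks, final 0.047 | Gain |
|---|---|---|---|---|---|---|
| Equal | 83.9% | 83.9% | 0.0 | 81.2% | 83.5% | 2.3 |
| Large site 8.8%, others 4–18% | 84.0% | 84.3% | 0.2 | 81.3% | 83.9% | 2.6 |
| Large site 8.3%, others 2–25% | 84.2% | 84.8% | 0.6 | 81.5% | 84.4% | 2.9 |
| Large site 11.9%, others 3.6% | 84.1% | 84.6% | 0.5 | 81.4% | 84.1% | 2.8 |
| Large site 4.7%, others 18.7% | 84.3% | 85.3% | 1.0 | 81.5% | 84.9% | 3.4 |

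A continuity-corrected CMH gives only 80.8% to 82.1% as a single test, so the word uncorrected matters.

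**4. Overall type I error with the looks, >66% rule ignored** (common PEP 4.6% to 10%).

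- Fisher, final 0.05: 0.035 to 0.041.
- CMH, final 0.05: 0.0506 to 0.0521, slightly over.
- CMH, final 0.047: 0.0475 to 0.0490; with Fisher at the looks and CMH at the end, 0.0468 to 0.0483.
- If the looks counted in both directions, about 0.046 would be needed (0.0476 to 0.0496).

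So Fisher's conservatism currently absorbs the looks, and a switch to CMH spends it.

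**5. If the >66% rule binds** (pancreatitis only; a stop under it without p < 0.005 counted as no success). Under the planned effect, the standard-dose arm is expected to hold 0.092/(0.092 + 0.046) = 66.7% of cases, so the rule triggers often: 63% of trials stop at a look. Power is then 34.2% to 34.5% with Fisher, 39.6% to 42.0% with CMH throughout, and 35.9% to 36.5% with Fisher at the looks and CMH at the end. Type I error with CMH at an unchanged 0.05 is 0.019 to 0.043.

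**6. Moderate-severe PEP, 4.4% vs 2.2%, at 0.05.** Fisher 45.1%, Pearson 51.3%, CMH 51.2% to 52.0%.

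**7. What the interval would look like.** If the planned rates are observed, the simulated stratified risk difference is 4.6 ± 3.0 points, about 1.6 to 7.6. The log risk ratio has SE √(0.908/47.7 + 0.954/23.8) = 0.24, giving a risk ratio of 0.50 with limits of about 0.31 and 0.81. Simulated coverage is 0.947 to 0.950 and 0.951 to 0.954 respectively.

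**8. Center in the multivariate model.** Expected events are 518 × (0.092 + 0.046) = 71.5, so about 7 of the 24 candidates can enter. With no effect there would be 1036 × 0.092 = 95 events and a cap of 9. Either way, center is not guaranteed a place.

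**The case against.** The strongest reply is that this is a preference. Fisher's test is valid after stratified randomization, suits the sample-size formula and exceeds the stated power. The mismatch with the randomization costs almost nothing: 0 to 1 point, and the upper end needs center differences that nothing in the documents supports. The rest of the gain is the familiar argument between Fisher and an uncorrected chi-square. The change also creates a small type I error problem that the plan does not have, which must then be repaired with a lower threshold, and it gives up guaranteed exact size. The multivariate model already yields an adjusted treatment effect. If the >66% rule is taken at its word, that rule matters far more than the choice of test.

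Most of this stands, and it limits the point to an optional improvement. Two parts do not dispose of it. The multivariate model does not guarantee adjustment for center, and it does not cover moderate-severe PEP. Nothing in the objection supplies the missing confidence interval. The >66% rule is a separate matter; it enters here only because it determines whether the final threshold needs lowering.

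**Conclusion.** The point holds, as something to consider. There is no error in size, power or sample size. Counting the looks and the lowered threshold, but ignoring the >66% rule, the uncorrected stratified test gains 2.3 to 2.6 points of power with equal or 4–18% center rates, and up to 3.4 with extreme ones. For moderate-severe PEP the gain is 6 to 7 points, which still leaves power near 50%. Most of the gain comes from dropping Fisher and little from stratifying. These power figures do not describe the full plan if the >66% rule binds: power is then far lower with either test. The absence of any planned interval is the firmer half of the point, because it depends on none of the assumed center rates.

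**What to change.** - Make the primary and the moderate-severe PEP analyses CMH tests stratified by center, stated to be without continuity correction. Keep Fisher's exact test as a sensitivity analysis.
- For each comparison, report a center-stratified risk difference or risk ratio with a 95% CI.
- Name the test used at the two looks, and state whether the >66% rule is treated as binding. If it is not, set the final primary threshold at about 0.047; this holds with either CMH or Fisher at the looks. If it is binding, 0.05 can stay and 0.047 would be conservative.
- Confirm overall type I error by simulation with the actual center sizes.

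The cost is SAP wording and one simulation before unblinding, with no extra patients or data. The price is that guaranteed exact size gives way to a size near nominal (0.049 to 0.051 in simulation for a single test at 0.05). The 0.047 threshold costs about 0.6 point of power (84.1% to 83.5% with equal center rates).

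If the sponsor prefers to leave the test alone, adding the center-stratified estimate and CI needs no change of test or threshold and should be done in any case.
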